7.1.2 MN₅₀ Titers for SARS-CoV-2

As the 2nd secondary objectives, neutralizing antibody response to the SARS-CoV-2 spike protein in previously vaccinated participants 18 to 49 years of age, the derived/calculated endpoints of MN₅₀ response will include:

- MN₅₀ GMT is calculated as the antilog of the mean of the log-transformed MN₅₀ titers at Days 1 and 29. MN₅₀ GMT will be summarized by the study vaccine group and visit day along with the corresponding 2-sided 95% CIs, by exponentiating the corresponding log-transformed means and their 95% CIs.
- GMFR_{Post/Pre} is calculated as the ratio of post-vaccination MN₅₀ GMT at Day 29 to pre-vaccination MN₅₀ GMT at the baseline (Day 1). Similar sample SAS code as IgG will be applied to estimate MN₅₀ GMFR_{Post/Pre} and corresponding 95% CIs.
- MN₅₀ GMTR between any two of study vaccine groups at Day 29 and the two-sided 95% CIs will be computed using analysis of covariance (ANCOVA), with the study vaccine group as the fixed effect and MN₅₀ titer at Day 1 (adjusted for intergroup variation in baseline [pre-vaccination] MN₅₀ titer) as the covariate under two-sided type I error rate of 0.05. No type I error rate adjustments will be made. The mean difference of all lots paired comparisons with their corresponding CI limits will then be exponentiated to obtain MN₅₀ GMTR and the corresponding 95% CIs. Similar sample SAS code as IgG will be applied to estimate MN₅₀ GMTR and corresponding 95% CIs.
- SCR is defined as proportion of participants who achieve seroconversion ≥ 4 -fold increase from baseline in MN₅₀ titers at Day 29. SCR in MN₅₀ titers with corresponding two-sided exact binomial 95% CIs will be calculated using the Clopper-Pearson method with similar sample SAS code as IgG.
- Two-sided 95% CIs of the difference of SCRs in MN₅₀ titers for all pairwise comparisons will be based on the Miettinen and Nurminen method with the similar sample SAS code as IgG.

7.1.3 hACE2 Receptor-binding Inhibition Titers for SARS-CoV-2

As the 3rd secondary objectives, antibody responses in a hACE2 receptor-binding inhibition assay to the SARS-CoV-2 spike protein in previously vaccinated participants 18 to 49 years of age, the derived/calculated endpoints of hACE2 response will include hACE2 GMTs, GMFR_{Post/Pre}, and SCR will be summarized overall and by the study vaccine group, and between-group hACE2 GMTR and difference of SCRs in hACE2 titers for all pairwise comparisons will be calculated using the same statistical methods applied for MN50 titers.

7.2 Analyses of Secondary Endpoint of Safety

As the secondary objective, safety data include MAAEs and AESIs (including myocarditis and/or pericarditis) through Day 29 (ie, 28 days after vaccine dose) and SAEs throughout the study. All safety analyses will be descriptive and conducted using the Safety Analysis Set. Missing data will not be imputed.

MAAEs are defined as AEs with medically attended visits, including hospital, emergency room, urgent care clinic, or other visits to or from medical personnel for any reason. AESIs include PIMMCs, myocarditis or pericarditis (Listings in Appendix 3), AEs specific to COVID-19, or other potential AEs that may be determined at any time by regulatory authorities as additional information concerning COVID-19 is obtained (Listings in Appendix 2). SAE is defined as an event considered “serious” if, in the view of either the Investigator or Sponsor, it results in any of the outcomes listed in Section 8.1 Protocol.

Unsolicited MAAEs and AESIs through Day 29, and SAEs throughout the study will be summarized overall and by the study vaccine group and by SOC/PT using the latest version of MedDRA, as well as by severity (Mild, Moderate, Severe, or Potentially Life Threatening) and relationship (not related, related) to the study vaccine to present the number and percentage with its corresponding exact 95% CIs using Clopper-Pearson method. For multiple occurrences of an AE in the same participant, a participant will be counted only once within an SOC or a PT, using the most severe occurrence and closest reported relationship for the summarization by severity or relationship to the study vaccine, respectively.

The duration of unsolicited AEs including MAAEs and AESIs through Day 29 will be summarized. A by-participant listing of MAAEs and AESIs through Day 29 and SAEs throughout the study will also be provided.

The following summaries of unsolicited AEs will be presented overall and by the study vaccine group as part of the primary analysis of safety:

- Overall summary of all unsolicited TEAEs (Days 1 - 29)
- Summary of all unsolicited TEAEs by MedDRA SOC/PT and severity (Days 1 - 29)
- Summary of all unsolicited TEAEs by MedDRA SOC/PT and relationship to study vaccine (Days 1 - 29)
- Summary of MAAEs by MedDRA SOC/PT and severity (Days 1 - 29)

- Summary of MAAEs by MedDRA SOC/PT and relationship to study vaccine (Days 1 - 29)
- Summary of AESIs (including PIMMCs, myocarditis or pericarditis, and complications to COVID-19) by MedDRA SOC/PT and severity (Days 1-29)
- Summary of AESIs (including PIMMCs, myocarditis or pericarditis, and complications to COVID-19) by MedDRA SOC/PT and relationship to study vaccine (Days 1-29)
- Summary of SAE by MedDRA SOC/PT and severity (Days 1-29)
- Duration of MAAEs (Days 1-29)
- Duration of AESIs (Days 1-29)
- Summary of unsolicited AEs leading to the discontinuation of study (Days 1-29)
- Summary of SAEs leading to the discontinuation of study (Days 1-29)
- Listings of all unsolicited AEs including MAAEs, AESIs (including PIMMCs, myocarditis or pericarditis and complications to COVID-19) and SAEs (Days 1-29)

7.3 Analysis of Exploratory Endpoints

The same statistical methods applied for the analysis of IgG, MN50, and hACE2 may also be applied to best characterize the immune response for future vaccine development needs to compare immune responses developed based on the assays used as the exploratory endpoints.

8 ADDITIONAL ANALYSES

8.1 Vital Signs

Vital sign measurements at all visits (Day 1 and Day 29) including respiratory rate, blood pressure, pulse rate and temperature (oral or via forehead/ear reader) will be summarized as continuous variables. Descriptive statistics for vital sign results and change from baseline in vital sign results will be presented overall and by the study vaccine group for all participants in the Safety Analysis Set, including means and SDs, median, minimum, and maximum. A by-participant listing of vital signs will be provided.

8.2 Physical Examinations

Physical examination at screening will include height and weight, HEENT, neck, lungs, heart, cardiovascular, abdomen, and musculoskeletal system/extremities to allow for study vaccination. Symptom-directed (targeted) physical examination performed at all other scheduled time points (Day 1 and Day 29) will be summarized by study vaccine group and by body system. For each body system examined, the number and percentage of participants with normal/abnormal results will be reported. The calculation of abnormal results will also be broken out by whether the abnormal result was considered clinically significant or not.

9 CONDUCT OF ANALYSES

After all participants have completed throughout the study (from Day 1 through Day 29), and their data are cleaned, an analysis of all primary/secondary endpoints (IgG, MN₅₀, and hACE2) and all secondary safety endpoints through Day 29 will be conducted.

10 COMPUTER METHODS

Statistical analyses will be performed using SAS[®] version 9.4 or higher in a Windows environment.

11 DATA HANDLING CONVENTIONS

All output will be incorporated into Microsoft Word or Excel files, or Adobe Acrobat PDF files, sorted and labeled according to the International Conference on Harmonisation (ICH) recommendations, and formatted to the appropriate page size(s).

Tabulations will be produced for appropriate demographic, baseline, and safety parameters. For categorical variables, summary tabulations of the number and percentage of participants within each category (with a category for missing data) of the parameter will be presented. For continuous variables, the number of participants, mean and standard deviation (SD), median, minimum, and maximum values will be presented.

All references to analysis of GMT/GMFR/GMTR/GMEU/GMEUR will be interpreted as analysis of the log₁₀ of titer values or ELISA Units.

The individual IgG ELISA Units, immunogenicity (MN₅₀) titer values and hACE2 receptor-binding inhibition titer values recorded as below the LLOQ of the assay will be set to half LLOQ for the purposes of GMT/GMFR/GMTR/GMEU/GMEUR analyses. The LLOQ values will be provided by corresponding labs.

Medical history and AEs will be coded using MedDRA Version 25.0.

Each parameter will be reported with the below defined decimal numbers in [Table 4](#).

Table 4 **Decimal Numbers for Parameters**

Parameter	Number of Decimal
Number of participants (e.g., N, N1, N2, n)	0
Percentage (%)	1
Mean	1 more decimal than raw data
Standard Deviation (SD)	1 more decimal than mean
Median, Min, Max	as same decimal as raw data
GMT, GMFR _{Post/Pre} , their corresponding 95% CIs	1
GMEU, GMFR _{Post/Pre} , their corresponding 95% CIs	1
GMTR, GMEUR, their corresponding 95% CIs	2
SCR (%), their corresponding 95% CIs	1

11.1 Baseline Definitions

For all analyses, baseline is defined as the last non-missing measurement prior to the first administration of the study material. For immunogenicity analysis, baseline will be the result from the sample drawn on the day of vaccination (Day 1).

11.2 Adjustments for Covariates

GMTR/GMEUR between the study vaccine groups for all pairwise comparisons will be adjusted for pre-vaccination titer/ELISA unit.

11.3 Multiple Comparisons/Multiplicity

No multiplicity adjustment will be applied for the immunogenicity primary and secondary endpoints.

11.4 Withdrawals, Dropouts, and Loss to Follow-up

Participants are free to withdraw from the study at any time upon written request. Participant participation in the study may be stopped at any time at the discretion of the investigator or at the request of the sponsor.

Participants may refuse further procedures (including study vaccination) but are encouraged to remain in the study for safety follow-up. In such cases where only safety is being conducted, participant contact could be managed via telemedicine contact (eg, telephone, web chat, video, FaceTime).

Participants who withdraw, are withdrawn or terminated from this study, or are lost to follow up after signing the informed consent form (ICF) but prior to first study vaccination may be replaced. Participants who receive study vaccine and subsequently withdraw, discontinue, are terminated from the study, or are lost to follow-up will not be replaced.

Whenever possible, any participant who withdraws from the study prematurely will undergo all EOS assessments. Any participant who fails to return for final assessments will be contacted by the site in an attempt to have them comply with the protocol.

11.5 Missing, Unused, and Spurious Data

The status of participants who fail to complete final assessments will be documented in the electronic case report form (eCRF). Data that would have been collected at subsequent visits will be considered missing.

When tabulating AE and Concomitant Medications (exclusive of vaccinations prior to Dose 1) data, partial dates of event onset will be handled as follows:

- If the day of the month is missing, the onset date will be assumed to be the date of the Day 1 vaccination or first of the month, whichever is later, in order to conservatively report the event as treatment-emergent.
- If the onset day and month are both missing, the event onset will be coded to the date of the Day 1 vaccination or 1st January of the year, whichever is later, in order to conservatively report the event as treatment-emergent.
- A completely missing onset date will be coded as the date of the Day 0 vaccination, unless the end date suggests it could have started prior to this in which case impute the 1st January of the same year as the end date.
- No imputations will be made to event ending dates.
- When imputing a start date ensure that the new imputed date is prior to the end date of the AE or medication.

When tabulating Medical History or Previous Vaccination data, partial start dates of event will be handled as follows:

- For start date with a missing day and/or month, impute a missing day as the first of the month, and a missing month as January. The resulting date should be prior to the Day 1 vaccination and before the end date (full or partial date). A partial start date with an entirely missing ending date should result in a query to the site.
- For start date with a missing year, impute the year to be year of the ending date if it exists. Otherwise, the missing start date will be kept as missing.

For tabulations of AE, a top-level summary will be generated to report treatment-related AEs according to two conventions:

- No imputation of missing relationship to test article
- Consider the event to be treatment-related to test article.

Similarly, the top-level summary will report severe AEs according to two conventions:

- No imputation of missing severity
- Consider the event to be severe

Detailed presentation of AE data by SOC and preferred terms will be generated without first imputing missing relationship nor severity. As with missing dates, queries to the site should be undertaken before employing the reporting conventions described above.

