6.2 Prior and Concomitant Medication and Vaccination

Prior medications include recent (≤ 90 days) and current medications and non-Covid-19 vaccinations. Concomitant medications will include all medications (including vaccines) taken by the participant from the time of signing the ICF through EOS (or through the early termination visit if prior to that time).

The number (percentage) of participants who record one or more prior/concomitant medications (including vaccines) recorded in the prior/concomitant medications eCRF will be summarized overall and by the study vaccine group and preferred drug name as coded using the WHO drug dictionary for all participants in the Safety Analysis Set. Multiple occurrences of medication usage for a participant will be counted only once within an anatomical therapeutic chemical (ATC) term and standardized medication name.

A by-participant listing of treatment-emergent new concomitant medications (including vaccines) will be presented.

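### The SAP's partial-date rule can never return a pre-vaccination onset, so records known to start in an earlier month or year become treatment-emergent

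*SAP*

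**What the plan says.** SAP 11.5 sets the scope: "When tabulating AE and Concomitant Medications (exclusive of vaccinations prior to Dose 1) data, partial dates of event onset will be handled as follows". Three onset rules follow.

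- Day missing, month and year known: "the onset date will be assumed to be the date of the Day 1 vaccination or first of the month, whichever is later".
- Day and month missing, year known: "the event onset will be coded to the date of the Day 1 vaccination or 1st January of the year, whichever is later".
- Whole date missing: "A completely missing onset date will be coded as the date of the Day 0 vaccination", with an exception that allows 1 January of the end-date year if the end date suggests an earlier start.

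The first two rules carry a stated purpose: "in order to conservatively report the event as treatment-emergent". A guard is added: "When imputing a start date ensure that the new imputed date is prior to the end date of the AE or medication". The closing paragraph of the section puts site queries ahead of imputation: "As with missing dates, queries to the site should be undertaken before employing the reporting conventions described above".

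The same section treats Medical History differently. A missing day becomes the first of the known month and a missing month becomes January, so the known part of the date is kept.

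One output depends directly on the imputed medication start. SAP 6.2 states: "A by-participant listing of treatment-emergent new concomitant medications (including vaccines) will be presented".

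**The concern.** Conservative imputation is sound when the recorded part of a date leaves open whether onset came before or after vaccination. It has no purpose when the recorded month or year already settles the matter. A drug recorded as started in 2015 and still taken is known not to be new, yet the rule gives it the vaccination date. That overwrites recorded information instead of handling a missing value.

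At stake is the accuracy of safety outputs. Long-standing medications would be listed as started after vaccination. A serious event that began before vaccination could also enter the Days 1 to 29 tables in SAP 7.2.

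**Working it through.** The plan states no figure to reproduce. The check applies the rules literally.

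**Inputs.** V is the Day 1 vaccination date. F is the first day of the known month, or 1 January of the known year (SAP 11.5). A record is treatment-emergent if its onset is on or after V (Protocol 8.2.3.1 for adverse events).

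**SAP rule.** Imputed onset = max(V, F). Since max(V, F) ≥ V for every F, the result is always treatment-emergent. Applying the rule to every month-and-year and year-only onset from 1990 to 2023, against every Day 1 date in 2022, gave no imputed date before Day 1.

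**Compatible-date rule, for comparison.** Use V only if the known month and year (or the known year, if the month is missing) equal those of V. Otherwise use F.

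Illustration with an assumed Day 1 of 15 Jul 2022 and no end-date conflict:

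| Recorded onset | SAP rule | Compatible-date rule |
|---|---|---|
| 2015 | 15 Jul 2022, emergent | 1 Jan 2015, prior |
| Mar 2019 | 15 Jul 2022, emergent | 1 Mar 2019, prior |
| 2021 | 15 Jul 2022, emergent | 1 Jan 2021, prior |
| May 2022 | 15 Jul 2022, emergent | 1 May 2022, prior |
| Jun 2022 | 15 Jul 2022, emergent | 1 Jun 2022, prior |
| Jul 2022 | 15 Jul 2022, emergent | 15 Jul 2022, emergent |
| 2022 | 15 Jul 2022, emergent | 15 Jul 2022, emergent |
| Aug 2022 | 1 Aug 2022, emergent | 1 Aug 2022, emergent |

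Only records whose known period lies wholly before Day 1 change. The last three rows, where conservatism has a role or onset is clearly later, are identical.

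**End-date guard.** Take onset Jun 2022, end 5 Jul 2022, Day 1 15 Jul 2022. The rule gives 15 Jul and the guard forbids it, but the SAP names no date to use instead. The guard does nothing for records that are ongoing or ended after Day 1.

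**Internal comparison.** Under the Medical History rule a condition dated 2015 becomes 1 Jan 2015, while the ongoing drug for it, also dated 2015, becomes Day 1. A wholly missing onset can be placed before vaccination through its end date; a recorded earlier month and year cannot.

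**Range for recent starts.** Assume true starts are spread evenly over the W days before Day 1, and let d be the day of the month of Day 1. The share falling in an earlier calendar month is (W − (d − 1)) / W.

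- W = 90 (the look-back for recent medications): d = 31 gives 60/90 = 67%; d = 1 gives 90/90 = 100%. The mean over 2022 dates is 84%.
- W = 30 (the longest screening window in the Schedule of Events): d = 31 gives 0/30 = 0%; d = 1 gives 30/30 = 100%. The mean is 51%.

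These shares apply only to records with a missing day that did not end before Day 1. They do not say how many such records there will be.

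**The case against.** The strongest reply is that the rule reaches little.

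- **Adverse events.** Protocol 8.2.2 sends occurrences that begin before vaccination to Medical History, and collects medically attended events and events of special interest only from vaccination. Serious events are the exception, being collected from consent. Protocol 6.1.1 expects Screening and Day 1 to be one visit, so that window should be very short for most participants. A reader might infer that the adverse event tables are broadly contaminated; these provisions do not support that. The remaining exposure is essentially a serious event between consent and vaccination, with its onset day missing, begun in an earlier calendar month and not ended before Day 1.
- **Medication summary.** A reader might infer that the division into prior and concomitant use is wrong. SAP 6.2 counts concomitant use from consent, includes current drugs under prior, and plans one pooled table counting each participant once per term. That count does not depend on the imputed start.
- **Queries first.** Sites are queried before any imputation, which should reduce the number of partial dates. The rule exists for those that remain.
- **No conclusion changes.** Safety analyses are descriptive, the rule is the same for all three lots, and its error runs towards over-reporting. The primary IgG analysis does not use these dates.

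All four points stand as limits on reach. None makes the rule correct for the records it does reach: recent and current medications are entered on the concomitant medication page (Protocol, Schedule of Events), so long-standing drugs are within scope.

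**Conclusion.** The rule is wrong for one defined class of record: onset still partial after query, known month or year wholly before vaccination, and ongoing or ended after Day 1. Every such record is misdated to Day 1. The main consequence is false entries in the listing of new medications. The secondary one is a small risk for pre-vaccination serious events, where one misplaced participant would add 1/300 = 0.33 percentage points to a lot.

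The conclusion assumes that the rule is programmed as written and that the data entry system accepts partial dates, as the rule itself presumes. It would be tempting to put a number on affected participants by applying a guessed share to the 900 planned. The documents give neither the frequency of partial dates nor the yield of queries, so no such figure is supported. The reference to a Day 0 vaccination is editorial: the study has a single vaccination, on Day 1.

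**What to change.** Amend SAP 11.5 as follows.

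1. Impute the Day 1 date only when the known month and year (or the known year, if the month is missing) equal those of the Day 1 vaccination.
2. Otherwise impute the first day of the known month or year. Earlier periods are then classed as pre-vaccination and later ones stay treatment-emergent.
3. If an imputed Day 1 date would fall after the recorded end date, use the first day of the known month or year instead. Word the guard as no later than the end date, so that a record ending on Day 1 does not conflict with it.
4. Replace the Day 0 reference with Day 1.

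The cost is a few SAP sentences and one date-imputation macro, with no change to data collection. It is best made before the safety listings are programmed.

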14 APPENDIX

Appendix 2 Schedule of Events for Study 2019nCoV-307

Study Day	–30 to 1 ¹	1 ¹	Unscheduled visit	29
Window (days)	–	–		+ 4
Study Visit	Screening	1		EOS ²
Informed consent	X			
Medical history ³	X			
Inclusion/exclusion criteria ⁴	X	X ⁴		
Demographics	X			
Prior/concomitant medications	X ⁵	X ⁶	X	X
Vital sign measurements	X	X ⁶	X	X
Urine pregnancy test (WOCBP)	X	X ⁶		
Physical examination	X	X ⁶	X	X
Baseline ECG		X ⁶		
Nasal swab at clinic for SARS-CoV-2 (PCR) – anterior nares		X ⁶		
Blood sampling for SARS-CoV-2 (ELISA for anti S-protein serology, MN ₅₀ assay, and hACE2 receptor-binding inhibition assay)		X ⁶		X
Randomization		X ⁶		
Vaccination		X ⁷		
SAEs	XX	X	X	X
All MAAEs and AESIs (including PIMMCs, myocarditis or pericarditis)] ⁸		X	X X	X
EOS form ⁹				X

Abbreviations: AESI = adverse event(s) of special interest; ELISA = enzyme-linked immunosorbent assay; EOS = end of study; hACE2 = human angiotensin-converting enzyme 2; MAAE = medically attended adverse event; MN₅₀ = microneutralization assay with an inhibitory concentration of 50%; PCR = polymerase chain reaction; PIMMC = potential immune-mediated medical conditions; S = spike (protein); SAE = serious adverse event; SARS-CoV-2 = severe acute respiratory syndrome coronavirus 2; WOCBP = women of childbearing potential.

1. The Screening visit and Day 1 visit may be combined if feasible at any given study site.
2. EOS assessments will be conducted via on-site visit. Should participants decide to terminate early, a telephone call may occur to collect the maximum safety data possible.
3. Significant medical history should be recorded, including prior and ongoing medical conditions and significant surgical procedures.
4. Specific exclusions to study vaccination will be assessed before any vaccination. Waivers to enrolling participants with exclusions will not be given.

5. Recent (≤ 90 days) and current medications, including non-COVID-19 vaccines, should be recorded in the concomitant medication eCRF. All COVID-19 vaccines administered prior to screening should be recorded in the vaccine history eCRF.
6. Performed prior to study vaccination.
7. On vaccination day, participants will remain in the clinic or under study staff observation for at least 15 minutes post-vaccination to be monitored for any immediate hypersensitivity reactions.
8. Recording of SAEs, MAAEs, and AESIs (including potential immune-mediated medical conditions [PIMMCs] and myocarditis or pericarditis). See Table 4 for symptoms of myocarditis or pericarditis and Section 8.2.3.6 for instructions for follow-up.
9. EOS form will be completed for all participants, including participants who are terminated early.

